2.1. Study Rationale

In the Phase 3 pivotal multiple daily injection studies (Blevins et al. 2020; Jinnouchi et al. 2020; Klaff et al. 2020), LY900014 dosed at the start of a meal demonstrated noninferior overall glycemic control (hemoglobin A1c [HbA1c]) in patients with T1D and type 2 diabetes mellitus, and superior overall glycemic control in patients with T1D, and consistently better postprandial glucose (PPG) control, compared to Humalog. Injection site reactions occurred at a higher incidence with LY900014 compared to Humalog (2.7% versus 0.1%, respectively), but had an overall low incidence.

LY900014 was efficacious, providing superior PPG control and less time in hypoglycaemia but with more frequent infusion site reactions (ISRs) compared with Humalog when administered by continuous subcutaneous insulin infusion (CSII) (Warren et al. 2021). Infusion site reactions were reported by 37.7% of T1D patients treated with LY900014 using CSII for 16 weeks in the PRONTO-Pump-2 study (Warren et al. 2021). Typically, local infusion site pain is noted immediately after infusion of a bolus dose, subsiding over 20-30 minutes thereafter.

This study aims to investigate whether local infusion site pain is dependent on the site of infusion and/or the depth of the infusion. In addition, the study will investigate the contribution of two of the excipients of LY900014 to local infusion site pain.

2.2. Background

Type 1 diabetes mellitus is an autoimmune disease resulting in destruction of beta cells, and lifelong dependency on exogenous insulin. The prevalence of T1D is near 1 in 300 and its incidence is steadily increasing worldwide (3% per year) (Gan et al. 2012).

Many advances in the treatment of T1D have occurred in the last 20 years; however, reaching and maintaining glycemic goals remains challenging even under intensive insulin therapy regimens. Rapid-acting insulin analogs, such as insulin lispro, aspart, and glulisine, were developed to be absorbed more rapidly and have a faster onset of insulin action compared with regular human insulin. Despite these improvements, the current formulations are not rapid enough to match carbohydrate absorption, limiting their efficacy in controlling PPG. LY900014 is a novel insulin lispro formulation developed to more closely match physiological insulin secretion and improve PPG control. In a recent publication comparing the pharmacokinetics and glucodynamics of LY900014 with Humalog, Fiasp®, and NovoRapid®, LY900014 showed greater numeric glucose lowering during a mixed meal tolerance test in patients with T1D and more closely matched the early glucose lowering of endogenous insulin secretion in healthy individuals (Heise et al. 2020; Leohr et al. 2020). Phase 3 clinical studies of LY900014 have demonstrated superiority of LY900014 to Humalog in controlling PPG excursions, with a similar

overall safety profile in patients with T1D (Klaff et al. 2020) and T2D (Blevins et al. 2020; Jinnouchi et al. 2020).

LY900014 is composed of the active ingredient insulin lispro and two locally acting excipients, treprostinil to induce local vasodilation and citrate to increase vascular permeability, thereby accelerating insulin lispro absorption. The LY900014 formulation also differs from the Humalog formulation in that it includes magnesium to stabilize the insulin. Treprostinil is a prostacyclin analog used in the treatment of pulmonary arterial hypertension. Treatment with high-dose continuous SC or intravenous infusion of treprostinil with clear systemic effects is known to be associated with injection/infusion site pain and injection/infusion site reactions (Remodulin SPC 2016). The clinically relevant doses of LY900014 administered via the SC route contain microdoses of treprostinil that are not detectable in the systemic circulation or associated with any systemic effects. However, local vasodilation at the injection site could potentially be a contributing factor to local erythema or discomfort. In addition, prostacyclins may be involved as endogenous mediators of inflammation and pain (Murata et al. 1997). **CCI**

Citrate has been associated with injection site pain in other injectable products (Humira Prescribing Information 2021; Kaiser et al. 2012; Nash et al. 2016). The specific role of citrate in LY900014 injection/infusion site reaction events is unknown, but increased local vascular permeability with injection/infusion of LY900014 could potentially contribute to injection/infusion site reactions. Further, evidence suggests that citrate chelation of endogenous divalent metal ions may lead to injection/infusion site pain, and reintroduction of magnesium can mitigate this discomfort (Krasner et al. 2012). **CCI**

CCI

In the PRONTO-Pump-2 study, most ISRs with LY900014 started in the first 4 weeks after randomization (Warren et al. 2021). The reported ISRs were primarily mild in severity (approximately 75%) and lasted a median of 2 to 6 days in this study. While individual ISRs resolved during the study, other events could occur with a different infusion set/site. Additional analysis determined there were no significant treatment-by-subgroup interactions for the incidence of ISRs for sex, age, body mass index (BMI), ethnicity, race, infusion set model, bolus speed, total daily dose, duration of diabetes, or duration of CSII use.

The Investigator's Brochure (IB) describes the clinical and nonclinical development of LY900014. Additional details are also available in the LY900014 package insert (Lyumjev SPC 2020).

2.3. Benefit/Risk Assessment

There is no direct clinical benefit anticipated from participation in this trial.

The treatments (sodium citrate, magnesium chloride, Humalog diluent, or treprostinil) within this study are administered below approved therapeutic levels and are considered placebo treatments. No known potential risks are associated with the use of small amounts of treprostinil, sodium citrate, magnesium chloride, or Humalog diluent. Furthermore, these study treatments are well characterized, and the description of each treatment relative to a therapeutic use is described in Section 8.4.

Potential risks associated with CSII pump use

- Minor skin irritation, sensitization, or localized inflammatory response can occur if skin contacts bioincompatible materials.
- Pain, bruising, swelling, redness, and bleeding at the infusion set insertion site.

The occurrence and severity of these events are not expected to be different from routine use of the Medtronic™ MiniMed™ 770G pump. More detailed information about the known and expected risks and potential adverse events may be found in the manufacturer's instructions.

3. Objectives and Endpoints

Objectives	Endpoints
Part A	
Primary	
To investigate local infusion site pain for infusions of sodium citrate and treprostinil in Humalog diluent with magnesium chloride (without insulin) in the abdominal, arm, thigh, and buttock areas in participants with T1D on CSII.	VAS pain score
Secondary	
To investigate local infusion site pain of 2 different cannula insertion depths (6 mm and 9 mm) in participants with T1D on CSII	VAS pain score
Exploratory:	
To assess local infusion site reactions using the exploratory CCI Platform	Characterization and measurement of incidence and severity of local infusion site reaction data

Abbreviations: CSII = continuous subcutaneous insulin infusion; VAS = visual analog scale; T1D = type 1 diabetes mellitus.

4. Study Design

4.1. Overall Design

Study I8B-MC-ITTC is a 1-/2-center, participant-(Part A CCI [REDACTED]) and investigator- CCI [REDACTED] blind, 2-part randomized crossover study in adults (18 to 69 years of age, inclusive) with T1D on CSII. Approximately 46 participants will be randomly assigned to study intervention such that approximately 40 evaluable participants complete Part A CCI [REDACTED] of the study. CCI [REDACTED]
[REDACTED]
[REDACTED]

Part A of this study will be a 1-/2-center, randomized, 1 day 5-period crossover based on the order of infusion sites and depths, blinded (between infusion depths), open-label single-treatment study conducted in adults with T1D.

CCI [REDACTED]
[REDACTED]

For CCI Part A CCI, the participant will continue using his or her personal insulin pump system at the currently employed infusion site and will be responsible for performing the required actions to maintain its functionality. Participants will be instructed to avoid the use of the central abdominal area for their personal infusion sets during the CCI [REDACTED] and prior to arrival at the clinical research unit (CRU).

For Part A

1. Following an informed consent and a screening visit, participants will come to the CRU in the evening (after dinner) of Day -1 for Part A.
2. Prior to the insertion of the first infusion set, the thickness of the SC adipose tissue layer at the abdomen, arm, thigh, and buttock areas will be assessed by ultrasound and recorded in the electronic case report form (eCRF). The evaluated site should be identified with a unique identifier.
3. The infusion sites will be assessed, and an image of each local infusion site will be collected using the CCI [REDACTED] Platform (Section 8.2.5.3.1) prior to insertion of the corresponding infusion set.
4. Each Medtronic™ MiniMed™ 770G pump reservoir will be filled by a qualified site staff member with 3 mL of study treatment (sodium citrate and treprostinil in Humalog diluent with magnesium chloride [without insulin]). The pump and infusion set will be set up as described in Section 6.1.1.
5. Five pumps will be used for each participant to assess infusions into the abdominal, arm, thigh, and buttocks areas. Participants will be randomly assigned to 1 of 5 infusion site sequences as shown in Table 4 to indicate the order of the infusion sites being evaluated.
6. Six mm cannula will be inserted into each of the designated areas (abdomen [at least 5 cm away from the umbilicus in the left or right lower quadrants], posterior aspect of the upper arm,

anterior or lateral thigh, and upper buttock), avoiding areas of lipohypertrophy or surgical scars. At the abdominal area only, a 9 mm cannula will also be inserted into the opposite side of the lower abdomen.

7. The first infusion site will be initiated, and a basal infusion rate of 1 U/h will be started. The same procedure will occur at the subsequent infusion sites according to the randomly assigned sequence with an approximately 30-minute interval between initiation of the previous infusion site. In case of immediate infusion set intolerance, a new infusion set can be inserted within the first 10 minutes of initiation of the infusion site.

Table 4 Infusion Site Sequences for Part A

	Infusion 1	Infusion 2	Infusion 3	Infusion 4	Infusion 5
Sequence 1	Arm	Thigh	Abdomen 6 mm	Abdomen 9 mm	Buttock
Sequence 2	Abdomen 6 mm	Abdomen 9 mm	Thigh	Buttock	Arm
Sequence 3	Abdomen 9 mm	Arm	Buttock	Abdomen 6 mm	Thigh
Sequence 4	Thigh	Buttock	Abdomen 9 mm	Arm	Abdomen 6 mm
Sequence 5	Buttock	Abdomen 6 mm	Arm	Thigh	Abdomen 9 mm

Note: This is an example table based on a 5x5 Latin square design; participants will be assigned an infusion sequence according to the actual schedule provided to the site.

8. Approximately 3 hours after the start of the basal infusion at 1 U/hr, a bolus dose of 15 U will be delivered at quick bolus speed (15 U/min) to each infusion site according to the treatment sequence with an approximately 30-minute interval between infusion sites.

9. A second bolus of 15 U given at quick speed (15 U/min) will be delivered approximately 6 hours after the start of the basal infusion to each infusion site according to the treatment sequence with an approximately 30-minute interval between infusion sites.

10. A third bolus dose of 15 U given at quick speed (15 U/min) will be delivered approximately 9 hours after the start of the basal infusion to each infusion site according to the treatment sequence with an approximately 30-minute interval between infusion sites.

11. Participants will rate the pain at each infusion site after each bolus dose at the following approximate time points: 5 minutes before the administration of a bolus dose and 1 and 15 minutes after the start of each bolus dose.

12. Study infusion sets with cannula and pumps will be removed.

[figure not shown]
13. Infusion sites will be evaluated for acute local infusion site reactions as described in Section 8.2.5.3 and an image of each local infusion site will be collected using the **CCI** Platform (Section 8.2.5.3.1).

14. Following the final evaluation, the participants will have the option to spend the night or be discharged from the CRU.

CCI

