6.3. Measures to Minimize Bias: Randomization and Blinding

Randomization and blinding will be used in order to avoid bias introduced through an association between allocation order and participant characteristics.

In Part A of this study, participants will be randomly assigned to 1 of 5 infusion site sequences to indicate the order of the infusion sites being evaluated. The infusion depths will be blinded.

CCI

The CRU personnel who will prepare the pump reservoirs for each treatment period will not be blinded and will be separate and distinct from those who are involved in subject care. The sponsor including the Lilly study team will be unblinded. Blinding will be maintained throughout the conduct of the study.

Treatment assignment will be kept strictly confidential and accessible only to authorized persons until after the time of unblinding. Codes with treatment assignment will, however, be readily available to the blinded personnel in case of an emergency.

If an investigator, site personnel performing assessments, or participant is unblinded, the participant must be discontinued from the study. In cases where there are ethical reasons to have the participant remain in the study, the investigator must obtain specific approval from a sponsor clinical pharmacologist or clinical research physician (CRP)/clinical research scientist (CRS) for the participant to continue in the study.

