9.3.2. Primary Endpoints

Infusion site pain assessed using the VAS pain score will be listed and summarized using standard descriptive statistics by bolus time (3, 6, and 9 hours after initiation of basal infusion) and VAS assessment time point (5 minutes prior to bolus and 1 and 15 minutes after bolus). For Part A, the summary will also be by infusion site location. The 5 infusion site locations include the assessment of 2 cannula depths at the abdominal site. CCI
[REDACTED]

CCI

A mixed effects model will be used to analyze from the log transformed VAS pain score for each bolus time and VAS time point. The statistical model for Part A will include terms for infusion site location, period (order of infusions), bolus time, VAS time point, the 2- and 3-way interactions between infusion site location, bolus time, and VAS time point as fixed effects and participant as a random effect. Comparisons will be made between infusion site locations and between cannula insertion depths for the abdominal infusion site for each bolus time and VAS time point. **CCI**

Least-squares means (LSMeans), infusion site location/treatment differences in LSMeans, and the corresponding 95% confidence intervals (CIs) for the infusion site location/treatment differences will be estimated and back-transformed from the log scale to provide estimates of the ratio of geometric LSMeans and 95% CI for the ratio of these means. It is possible that VAS scores will be 0; if so, all scores may be updated to log (VAS+1) to allow for the inclusion of the 0 values in the analysis.

The same model will also be used to analyze the change from the pre-bolus time point (5 minutes prior to the bolus) to the post-bolus time points of (1 and 15 minutes after bolus).

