5.1 PART A

1. Following an informed consent and a screening visit, participants will come to the CRU in the evening (after dinner) of Day -1 for Part A.
2. Prior to the insertion of the first infusion set, the thickness of the SC adipose tissue layer at the abdomen, arm, thigh, and buttock areas will be assessed by ultrasound and the measurement recorded in mm in the electronic case report form. The evaluated site should be identified with a unique identifier.
3. The infusion sites will be assessed, and an image of each local infusion site will be collected using the CCI [REDACTED] Platform prior to insertion of the corresponding infusion set.
4. Each Medtronic™ MiniMed™ 770G pump reservoir will be filled by a qualified site staff member with 3 mL of study treatment (sodium citrate and treprostinil in Humalog diluent with magnesium chloride [without insulin]).
5. Five pumps will be used for each participant to assess infusions into the abdominal, arm, thigh, and buttocks areas. Participants will be randomly assigned to 1 of 5 infusion site sequences to indicate the order of the infusion sites being evaluated.
6. Six mm cannula will be inserted into each of the designated areas (abdomen [at least 5 cm away from the umbilicus in the left or right lower quadrants], posterior aspect of the upper arm, anterior or lateral thigh, and upper buttock), avoiding areas of lipohypertrophy or surgical scars. At the abdominal area only, a 9 mm cannula will also be inserted into the opposite side of the lower abdomen.

7. The first infusion site will be initiated, and a basal infusion rate of 1 U/h will be started. The same procedure will occur at the subsequent infusion sites according to the randomly assigned sequence with an approximately 30-minute interval between initiation of the previous infusion site. In case of immediate infusion set intolerance, a new infusion set can be inserted within the first 10 minutes of initiation of the infusion site.
8. Approximately 3 hours after the start of the basal infusion at 1 U/hr, a bolus dose of 15 U will be delivered at quick bolus speed (15 U/min) to each infusion site according to the treatment sequence with an approximately 30-minute interval between infusion sites.
9. A second bolus of 15 U given at quick speed (15 U/min) will be delivered approximately 6 hours after the start of the basal infusion to each infusion site according to the treatment sequence with an approximately 30-minute interval between infusion sites.

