Least-squares means (LSMeans), infusion site location/treatment differences in LSMeans, and the corresponding 95% confidence intervals (CIs) for the infusion site location/treatment differences will be estimated and back-transformed from the log scale to provide estimates of the ratio of geometric LSMeans and 95% CI for the ratio of these means. It is possible that VAS scores will be 0; if so, all scores will be analyzed as log (VAS+1) to allow for the inclusion of the 0 values in the analysis.

The same model will also be used to analyze the change from the pre-bolus time point (5 minutes prior to the bolus) to the post-bolus time points of (1 and 15 minutes after bolus).

Example SAS code for Part A is shown below, CCI

```
proc mixed data=xxxx;
class location period bolus_time vas_time subjid;
model logVAS = period location|bolus_time|vas_time /residual ddfm=kr2;
random intercept / subject=subjid;
lsmeans location*bolus_time*VAS_time / cl pdiff alpha=0.05;
ods output lsmeans=lsm;
ods output diff=estims;
run;
```

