9.3.2 Secondary Endpoint

For Part A, the comparison of cannula depths at the abdominal infusion site location will be analyzed as part of the same mixed effects model used for the primary endpoint.

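### Five sequences cannot balance which infusion site directly precedes which in Part A; ten would at almost no cost, although harm from using five is not shown

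*Protocol*

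**What the plan says.** Part A compares five conditions in each participant on one day: arm, thigh, buttock, and abdomen at 6 mm and at 9 mm. Protocol 4.1 (Part A, step 5) states "Participants will be randomly assigned to 1 of 5 infusion site sequences as shown in Table 4". Protocol 6.3 repeats that "participants will be randomly assigned to 1 of 5 infusion site sequences to indicate the order of the infusion sites being evaluated", and SAP 5.1, step 5, has the same sentence without the reference to a table. The note under Table 4 reads "This is an example table based on a 5x5 Latin square design; participants will be assigned an infusion sequence according to the actual schedule", so the real list is not in the documents, but the number of sequences is.

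In Protocol 1.3, Table 2, boluses at successive sites are 30 minutes apart, each with a window of 3 minutes either way. Each site is rated 5 minutes before its bolus and 1 and 15 minutes after the bolus starts. Protocol 2.1 says that pain after an LY900014 bolus typically fades over 20 to 30 minutes.

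The model in SAP 9.3.1 is "model logVAS = period location|bolus_time|vas_time /residual ddfm=kr2", with a random participant intercept. It has period but no term for the preceding site. SAP 9.3.2 says that "the comparison of cannula depths at the abdominal infusion site location will be analyzed as part of the same mixed effects model". Protocol 9.3.2 and SAP 9.3.1 also plan an analysis of change from the pre-bolus rating. The visible text of neither document discusses carryover or balance of preceding sites.

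**The concern.** A Latin square gives every site each position once, which protects against drift over the day. It does not ensure that each site follows every other site equally often. If a recent bolus at one site changes the rating at the next, through lingering pain or through contrast in how the participant uses the scale, and if that effect differs by preceding site, it leaks into the site comparisons (primary) and the depth comparison (secondary).

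The pre-bolus rating is the most exposed, because it falls closest to the previous site's bolus. It is also the reference for the change analysis, so an inflated pre-bolus value enters there with reversed sign.

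**Working it through.** **The plan's own figure.** Inputs from Protocol 9.5: 40 completers, ratio 1.55 (ln 1.55 = 0.438), SD of the within-participant log difference 0.95, two-sided alpha 0.05. A paired t-test gives 81.2% power, which agrees with the stated 80%. The standard error of a contrast is 0.95/√40 = 0.150.

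**Timing.** Two successive boluses are 30 ± 6 minutes apart. Measured from the previous site's bolus, the next site's ratings fall at:
- pre-bolus (−5 ± 2): nominally 25 minutes, range 17 to 33
- +1 minute: nominally 31, range 25 to 37
- +15 minutes (± 2): nominally 45, range 37 to 53

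Only the pre-bolus rating nominally falls inside the 20 to 30 minutes.

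**Balance.** Five sequences hold 5 × 4 = 20 neighbouring pairs, and there are 5 × 4 = 20 ordered pairs of sites, so balance needs each pair exactly once. None of the 56 reduced 5x5 Latin squares achieves this (relabelling sites or reordering rows does not change balance), nor does any other set of five sequences. In Table 4, five ordered pairs occur twice (arm–thigh, thigh–buttock, buttock–6 mm, 6 mm–9 mm, 9 mm–arm), their five reverses never, and ten once.

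**Bias under Table 4.** Let c(site) be the log carryover into the next site, and assume none into the first site of a round, which comes 60 minutes after the last bolus of the previous round. With complete data a site contrast is a difference of site means:
- 9 mm is preceded by 6 mm twice, buttock once, thigh once, and is first once: [2c(6 mm) + c(buttock) + c(thigh)]/5
- 6 mm is preceded by buttock twice, thigh once, arm once, and is first once: [2c(buttock) + c(thigh) + c(arm)]/5
- 9 mm minus 6 mm: 0.4c(6 mm) − 0.2c(arm) − 0.2c(buttock)

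The weights sum to zero, so carryover equal from all sites cancels. That follows from each site occupying each position equally often.

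**Bias with ten sequences.** Every site follows every other site twice in ten, so contrast i minus j keeps only −0.2[c(i) − c(j)]. No third site enters.

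**Scenario: carryover c after either abdominal site, 0 after the others.** Absolute log error:

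| Contrast | Table 4 | Ten sequences |
|---|---|---|
| 9 mm vs 6 mm (depth) | 0.4c | 0 |
| arm vs buttock | 0.4c | 0 |
| arm vs thigh | 0.2c | 0 |
| thigh vs buttock | 0.2c | 0 |
| arm vs 6 mm | 0.6c | 0.2c |
| thigh vs 6 mm | 0.4c | 0.2c |
| buttock vs 6 mm | 0.2c | 0.2c |
| arm vs 9 mm | 0.2c | 0.2c |
| buttock vs 9 mm | 0.2c | 0.2c (sign flips) |
| thigh vs 9 mm | 0 | 0.2c |

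The documents give no c. As an assumption, let a fraction L of a 55% excess carry over, so c = 0.438L. For L = 0.1, 0.2 and 0.5:
- 0.6c is a false ratio of 1.03, 1.05, 1.14
- 0.4c is 1.02, 1.04, 1.09, with type I error 5.2%, 5.6%, 9.0% by normal approximation with SE 0.150
- 0.2c is 1.01, 1.02, 1.04

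**Without choosing a scenario.** If the five carryovers are independent with equal variance, the RMS bias is their SD times the root sum of squared weights. Under Table 4 this runs from √(0.4² + 2 × 0.2²) = 0.49 (depth, for example) to √(0.4² + 4 × 0.2²) = 0.57 (arm vs 6 mm, for example). With ten sequences it is √(2 × 0.2²) = 0.28 for every contrast.

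**Cost of a preceding-site term.** With 40 completers the variance of a contrast rises by a factor of 1.192 to 1.272 under Table 4 (SE +9% to +13%, power 74.1% to 71.3%) and by 1.056 with ten sequences (SE +2.7%, power 79.1%).

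**The case against.** A position-balanced Latin square with period fitted is a standard crossover design. Carryover here is not residue at one site: each site has its own pump and cannula, each rating names its site, and for the two abdominal cannulas "a 9 mm cannula will also be inserted into the opposite side of the lower abdomen" from the 6 mm one. The 20 to 30 minutes in Protocol 2.1 refers to LY900014, whereas the study fluid contains no insulin, and both post-bolus ratings nominally fall after that interval. All of this stands. It makes the mechanism uncertain, though it does not rule it out for the pre-bolus rating.

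It also stands that Table 4 is only an example. In the abdominal scenario the depth error is 0.2c times (how often 6 mm directly precedes 9 mm, minus the reverse). Table 4 gives 0.2c × (2 − 0) = 0.4c, but five of the ten site pairs in this square precede each other once each way, so half of all relabellings give a depth error of 0. A reader might infer from the 9.0% that the depth test in this trial has inflated type I error. The documents do not support that: the figure needs the example labelling and half of a 55% excess passing to another body site.

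A reader might also infer that ten sequences help every comparison. They do not. In the scenario above, thigh versus 9 mm goes from 0 to 0.2c, three other abdomen-versus-other contrasts keep the same size, and the average abdomen-versus-other contrast is off by 0.2c either way. If only the 9 mm site carries over, the depth error goes from 0 under Table 4 to 0.2c.

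**Conclusion.** The imbalance is certain and holds for any five-sequence schedule; its effect is not known. Equal carryover does no harm. Unequal carryover would bias site and depth contrasts, by amounts that are small unless carryover is large. Which contrast suffers most depends on the actual list, so the weights above apply to Table 4 only.

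The case for ten sequences is that they remove contamination from third sites, reduce the worst error in the abdominal scenario from 0.6c to 0.2c, and roughly halve the RMS bias of every contrast when carryovers are independent with equal variance. They also make a preceding-site analysis affordable. The results assume complete data and carryover only from the directly preceding site within a round. The documents do not show that the planned comparisons are biased. This is an improvement to consider, of low urgency but very low cost.

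**What to change.** Before enrolment, change five sequences to ten in Protocol 4.1, Protocol 6.3 and SAP 5.1, and update Table 4 and its note. Table 4 plus its own rows read right to left is a suitable design. The added rows are:
- 6: Buttock, Abdomen 9 mm, Abdomen 6 mm, Thigh, Arm
- 7: Arm, Buttock, Thigh, Abdomen 9 mm, Abdomen 6 mm
- 8: Thigh, Abdomen 6 mm, Buttock, Arm, Abdomen 9 mm
- 9: Abdomen 6 mm, Arm, Abdomen 9 mm, Buttock, Thigh
- 10: Abdomen 9 mm, Thigh, Arm, Abdomen 6 mm, Buttock

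Every ordered pair then occurs twice and every site appears twice in each position. If the actual schedule is a different square, do not simply mirror it: only 3 of the 56 reduced squares become balanced that way. Use Table 4 or another verified ten-sequence Williams design. In SAP 9.3.1, add a sensitivity analysis with a preceding-site term.

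The cost is a longer randomisation list. Participants, visits, boluses and planned-model power do not change. Balance is exact within each bolus round only: across all three rounds, counting the 60-minute step between rounds, ordered pairs occur 6 or 8 times (0 to 6 with five sequences). Each sequence has about 40/10 = 4 completers instead of 8, so an unreplaced dropout or an excluded site disturbs balance somewhat more. The Protocol 9.5 rule that a replacement takes the same sequence helps, but replacement is discretionary, and 46 divides evenly by neither 5 nor 10.
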